# 1 INTRODUCTION

## 1.1 Vaccines and non-specific effects

WHO recommends home visits after birth to reduce neonatal mortality. Guinea-Bissau has not implemented such home visits yet. Vaccinations are normally provided at the health centre, the current vaccination policy is to provide Bacillus Calmette-Guérin vaccine (BCG) and oral polio vaccine (OPV) at birth, pentavalent vaccine (diphtheria-tetanus-pertussis-H. influenzae type B-Hepatitis B vaccine), OPV and pneumococcal vaccine at 6, 10, and 14 weeks, rota-virus vaccine at 6 and 10 weeks, inactivated polio vaccine at 14 weeks, and measles vaccine (MV) and yellow fever vaccines at 9 months (Figure 1).

BCG: Bacillus Calmette-Guérin vaccine, OPV: Oral Polio vaccine

Penta: Diphtheria, Pertussis, Tetanus, Haemophilus Influenzae B, Hepatitis B

PCV: Pneumococcal vaccine, Rota: Rotavirus vaccine, IPV: Inactivated Polio Vaccine

MV: Measles vaccine, YF: Yellow Fever vaccine

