## 5.2 Study design and randomisation

We will conduct a cluster-randomised trial, randomising clusters to two different treatment groups, stratified by region and pre-trial mortality level (high/low). Pre-trial mortality level is assessed using the BHP rural HDSS data from 2012 to 2015. Pre-trial mortality level in the urban area will be based on the BHP urban HDSS data from 2013 to 2016, to account for a change in the registration system in 2012.

Randomisation of clusters will be by computer generated random numbers. All new-borns will be visited as soon as possible after birth. To children in half of the clusters we will provide standard care and vaccines (BCG, OPV) at the home visits; children in the remaining clusters will only receive standard care but no vaccines (Table 1).

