#### 5.5.2 Secondary outcomes

Through analyses of the secondary outcomes, we will try to gain a better knowledge of the effects of BCG and OPV. We will investigate, whether BCG and OPV affects severe morbidity:

- Non-accidental hospital admission. Hospital admission is defined as an overnight stay in a health facility. At the follow-up visits, the mother/guardian is asked, whether the child has been hospitalised. A special questionnaire is completed for each case of hospital admission to obtain information on timing, symptoms, duration and place of admission.
- Combined non-accidental mortality and non-accidental hospital admissions – severe morbidity defined as a composite outcome of mortality and first hospital admission.

Furthermore, we will assess the effect of BCG and OPV on other child-health-related outcomes:

- All-cause consultations
- Growth
  - Mid-upper-arm circumference
  - Weight-for-age z-score
- BCG scarring
- Cost-effectiveness of providing BCG and OPV at home visits
  - The cost of seeking vaccinations in rural Guinea-Bissau and the costs of consultations and hospitalisations are currently being evaluated in other studies. We will study the cost-effectiveness of providing BCG and OPV at a home visit using the effects on mortality and hospital admission from the present project.

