## **8 ETHICAL CONSIDERATIONS**

BCG is recommended at birth but vaccination is often delayed; in rural Guinea-Bissau most children receive BCG when aged >1month. While there may now be increasing acceptance that BCG has beneficial non-specific effects, we are still a long way from altering the implementation of the vaccination programme. The proposal compares two ways of delivering BCG and both will be an improvement relative to the current situation, where less than 40% of all infants get BCG during the first month of life. Hence, no child will receive BCG later than it would have done, had the trial not been carried out.

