## **9 IMPLICATIONS**

WHO recommends BCG at birth for normal-birth-weight children. However, due to the focus on not wasting vaccine doses BCG vaccination is delayed in many low-income countries. WHO recommends three home visits after birth, which is resource demanding and not implemented in many low-income countries. It is not recommended that the home visits are utilised for early vaccination. If we can confirm our hypothesis of reduced early infant mortality by providing BCG and OPV at a single home visit, this should be included in the WHO recommendations, and it will be an incentive for countries to introduce a single home visit with vaccines. In countries, where home visits are already in place, vaccines can easily be added to reduce early infant mortality.

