Growth measures	Weight will be analysed using the WHO weight-for-age z-score
Statistical tool	Linear regression
Adjustment	We will adjust the analysis for weight-for-age at enrolment, sex, region and pre-study mortality level
Clustering	We will use robust standard errors to account for clustering within village cluster

Stata code	Regress w-z-score random w-z-enrol sex b1.reg prmorlev, vce(cl regam) *w-z-score=weight-for-age z-score at first visit by the mobile teams, w-z-enrol=weight-for-age z-score at enrolment, reg=region, prmorlev=pre-study mortality level, regam=village cluster
------------	---

BCG scarring

Table 12: BCG scarring

Population	Identical to primary analysis of primary outcome
Observation timepoint	First visit after 6 months of age
Failure definition	Scar (yes/no)
Statistical tool	Log-binominal regression
Adjustment	We will adjust the analysis for sex, region and pre-study mortality level
Clustering	We will use robust standard errors to account for clustering within village cluster
Stata code	Binreg scar random sex b1.reg prmorlev, rr vce(cl regam) *reg=region, prmorlev=pre-study mortality level, regam=village cluster

Cost-effectiveness of providing BCG and OPV at birth

A cost effectiveness analysis seeking to measure the cost per death averted using a societal perspective will be performed, contrasting the costs of vaccine provision in the present programme and an outreach system as tested in the trial. The costs/savings associated with different rates of consultations and admissions will also be taken into account.

Suppurative lymphadenitis

We will assess the incidence of suppurative lymphadenitis as a reaction to BCG vaccination in the intervention and control clusters. Other serious adverse events to the BCG and OPV vaccine will be captured through the outcome measures (mortality, hospital admission and consultations).

5 Sensitivity analyses to test for robustness of conclusions

Table 13: Cause-specific death

Population	Identical to primary analysis of primary outcome
Observation period	From: Enrolment visit or 24 hours after birth, whichever comes last To: 60 days of life Censoring, first of:

	
 - Visit by the BHP - 60 days - Death due to accident - Date of registering first non-trial vaccine given after enrolment - Migration (migration out of the study area as per HDSS definition)
Time scale	Age

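### The planned cost per death averted charges the home-visit system to an effect that excludes the visit, so it is correct only if the visit alone does not change mortality, which the plan never states

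*SAP*

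**What the plan says.** Cost-effectiveness is a listed secondary outcome. The SAP describes it in two sentences (Appendix 2, section 4). The measure is set by "A cost effectiveness analysis seeking to measure the cost per death averted using a societal perspective will be performed", and the cost comparison by "contrasting the costs of vaccine provision in the present programme and an outreach system as tested in the trial". Savings or costs from different rates of consultation and admission are to be added. No cost items are listed, and the SAP text does not say where the number of deaths averted comes from.

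Protocol 5.5.2 supplies that: the analysis will study "the cost-effectiveness of providing BCG and OPV at a home visit using the effects on mortality and hospital admission from the present project".

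On what each arm receives, protocol 5.2 says "All new-borns will be visited as soon as possible after birth". Protocol 5.4.2 and Table 1 give both arms examination, weighing, advice on keeping the child warm, and cord care. The intervention arm also receives BCG and OPV; the control arm is told where vaccination can be had.

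On the present programme, protocol 1.1 says that vaccines are normally given at health centres and that "Guinea-Bissau has not implemented such home visits yet". Protocol section 8 makes the same distinction about the trial's arms: "The proposal compares two ways of delivering BCG and both will be an improvement relative to the current situation".

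**The concern.** A cost-effectiveness ratio needs the same two alternatives above and below the line. Here the cost difference is between outreach and a programme without visits, while the effect difference is between two arms that were both visited. The visit is paid for in the numerator and its effect is absent from the denominator.

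The resources are not trivial in kind. Protocol 5.1.3 and 5.1.4 describe a project motorbike, a nurse salary subsidy, a subsidy per visit, and a payment per timely birth notification. All of them serve control clusters as well as intervention clusters.

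Cost per death averted is a figure that a ministry could take at face value. If the visit itself saves lives, the planned ratio makes outreach look more expensive per death averted than it is; if the visit does harm, it makes outreach look cheaper. Nothing in the plan would alert the reader to either.

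**Working it through.** The documents state no cost, no number of deaths averted and no cost-effectiveness ratio, so there is no figure to reproduce. The check is to line up the comparators and then illustrate the size.

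**Comparators**

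- Numerator (SAP Appendix 2, section 4): cost of outreach with vaccines minus cost of the present programme, which has no visit.
- Denominator (protocol 5.5.2 with 5.2, 5.4.2 and Table 1): deaths with visit only minus deaths with visit plus vaccines.

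The second alternative in the two lines differs: no visit in one, visit without vaccines in the other.

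**Inputs for the illustration**

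- r: risk of death under the present programme. It cancels.
- h: proportional reduction from the visit alone. Protocol 5.3 quotes 8% (-12 to 25%) from a trial in Ghana of three visits in the first week, for neonatal mortality. This trial makes one visit and follows children to at most 60 days, so the figure is only a proxy.
- v: proportional reduction from the vaccines. It is 40% in the hypothesis (protocol section 4). A value of 20% is my assumption, added for sensitivity.
- Assumptions: the two effects multiply, and net cost is held fixed.

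**Formulas**

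- Deaths averted in the trial contrast: (1 - h) × v × r.
- Deaths averted against the present programme, which is what the costs describe: [1 - (1 - h)(1 - v)] × r.
- Planned ratio divided by matched ratio, at fixed net cost: the second quantity divided by the first.

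| h | v | Trial contrast (× r) | Matched to the costs (× r) | Factor |
|---|---|---|---|---|
| 0 | 0.40 | 0.400 | 0.400 | 1.00 |
| 0.08 | 0.40 | 0.92 × 0.40 = 0.368 | 1 - 0.92 × 0.60 = 0.448 | 1.22 |
| 0.25 | 0.40 | 0.75 × 0.40 = 0.300 | 1 - 0.75 × 0.60 = 0.550 | 1.83 |
| -0.12 | 0.40 | 1.12 × 0.40 = 0.448 | 1 - 1.12 × 0.60 = 0.328 | 0.73 |
| 0.08 | 0.20 | 0.92 × 0.20 = 0.184 | 1 - 0.92 × 0.80 = 0.264 | 1.43 |
| 0.25 | 0.20 | 0.75 × 0.20 = 0.150 | 1 - 0.75 × 0.80 = 0.400 | 2.67 |
| -0.12 | 0.20 | 1.12 × 0.20 = 0.224 | 1 - 1.12 × 0.80 = 0.104 | 0.46 |

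The smaller the vaccine effect, the more the result depends on the visit effect. The direction is not fixed: the factor exceeds 1 when the visit saves lives and falls below 1 when it does harm.

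The table takes the deaths averted directly from the difference between the trial arms. If the model instead applied the trial hazard ratio to present-programme mortality, the denominator would be v × r = 0.40r. At v = 0.40 the factor would then be 0.448/0.40 = 1.12, with a range of 0.328/0.40 = 0.82 to 0.550/0.40 = 1.38. That is smaller but has the same cause. The plan does not say which would be done.

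Savings from consultations and admissions, if taken from the trial arms, carry the same mismatch. Net cost would therefore not stay exactly fixed.

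**The case against.** The strongest reply is that the SAP names a real decision. Guinea-Bissau has no home visits, so outreach against the present programme is its own choice, and the cost side fits it. The only visit estimate in the documents has an interval that includes zero. With no visit effect the planned ratio is exactly right, and at the 8% point estimate it is conservative, because it charges the full outreach cost and credits only the vaccines. This stands as far as it goes. A reader might infer that the ratio matches no policy choice at all; the documents do not support that, because it matches this choice under a zero visit effect. What remains is that the assumption is unstated and untested, and that the same interval reaches -12%, where the ratio is no longer conservative.

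A second reply is that the costs of vaccine provision might be meant narrowly, without the visit system. No cost items are listed, so this cannot be excluded. But the SAP refers to the outreach system as it was tested, which points the other way. If the narrow reading is meant, the SAP should say so.

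Two other stronger readings should be resisted. A reader might infer that the protocol's implications section rests on this ratio when it says that "it will be an incentive for countries to introduce a single home visit with vaccines". That section is conditional on confirming the mortality hypothesis and does not mention cost-effectiveness; at most it shows that two policy settings are in view. A reader might also infer that the ratio is far too high for countries where visits already exist. The SAP does not offer it for those countries, and without any cost figure the size cannot be judged.

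**Conclusion.** The mismatch is real on the natural reading of the SAP taken together with protocol 5.5.2. The cost per death averted is correct for outreach against the present programme only if the visit alone has no effect on mortality, and neither document states that assumption.

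The factor of 1.22 (0.73 to 1.83) is an illustration. It rests on a visit effect from three visits and neonatal deaths in another country, the hypothesised 40% vaccine effect, multiplicative effects, fixed net cost, and deaths averted taken as the difference between the arms. It shows that the unstated assumption can matter in either direction; it does not estimate the error.

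The point concerns one secondary outcome. Randomisation, the primary analysis and participant safety are unaffected. It is still worth correcting before the analysis, because the change is small and the ratio would otherwise be reported without its main condition.

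**What to change.** In SAP Appendix 2, section 4, replace the single comparison with two, each using the same alternatives for costs and effects, and label each with the policy choice it answers:

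- **(a) Adding vaccines to a visit that already takes place.** Home visit with vaccines against home visit without. Use the trial effect and only the cost difference between the arms: vaccine, wastage from opened vials, supplies, vaccination time, consultations and admissions.
- **(b) Introducing outreach.** Outreach with vaccines against the present programme. Use full outreach costs and the trial effect, and state the visit effect explicitly, either zero as the base case or an outside estimate. Vary it over the range in protocol 5.3 (-12 to 25%), and note that the range comes from three visits and neonatal deaths.

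List the cost items in each contrast, say whether the trial effect enters as a risk difference or as a hazard ratio applied to a stated baseline risk, and add a matching sentence to protocol 5.5.2. Which contrast comes first is the sponsor's choice.

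The cost is SAP and protocol wording, an itemised cost list and one extra model scenario. No new outcome data and no change to trial conduct are needed. The drawback is that (b) depends on an assumed or outside visit effect and will look less certain than the single planned ratio.

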#### 5.7.7 Sensitivity analyses

In sensitivity analyses, we will assess whether the conclusions are robust to censoring at general health intervention campaigns, and whether we can identify if OPV and BCG prevents cause-specific hospitalisations or deaths (for details, see appendix: analysis plan).

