Statistical tool	Cox proportional hazards model
Stratification	We will employ models that allow for different baseline hazards according to sex, region and pre-study mortality level
Clustering	We will use robust standard errors to account for clustering within village cluster
Outline stata code For analysis: For model checking:	<pre> stset outdate, f(dead==1) enter (max(dob+1, date_enrol) /// exit (min (dnasc+60, date_mobileteam) origin(dob) stcox random, strata(sex reg prmorlev) vce(cl regam) estat phtest, detail† stphplot, strata(random) adj(sex reg prmorlev) stcox random, strata(sex reg prmorlev) vce(cl regam) tvc(random) texp(_t) *reg=region, prmorlev=pre-study mortality level, regam=village cluster </pre>

† If the proportional hazards assumption is not fulfilled we will still report the marginal hazard ratio but it will be supplemented by hazard ratios for two-three categorized time periods.

3 Effect-modifier analyses of primary outcome

We will assess whether the effect of the intervention on the primary effect measure is modified by the following potential effect modifiers.

Table 3. Sex as a potential effect modifier of the primary outcome

Potential effect modifier	Sex
Design	We will perform the analysis as describe above (for the primary analysis) allowing the effect of the intervention to differ between the sexes.
Reasoning	Previous studies have found sex-differential non-specific effects ^{1 2} , therefore, we will assess the sex-differential effects.
Outline stata code: For analysis: For model checking:	<pre>stcox random#sex sex, strata(sex reg pmorlev) vce(cl regam) contrast random#sex estat phtest, detail† stphplot, strata(random_sex) adj(sex reg pmorlev) stcox random#sex sex, strata(sex reg pmorlev) vce(cl regam) /// tvc(random#sex sex) texp(_t) *reg=region, pmorlev=pre-study mortality level, regam=village cluster, random_sex=a four-level variable based on the four possible combinations of random and sex</pre>

† If the proportional hazards assumption is not fulfilled we will still report the marginal hazard ratio but it will be supplemented by hazard ratios for two-three categorized time periods.

Table 4. Maternal BCG scar as a potential effect modifier of the primary outcome

Potential effect modifier	Maternal BCG scar (yes/no)
Design	We will perform the analysis as described above (for the primary analysis) allowing the effect of the intervention to differ by maternal BCG-scar status

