Clustering	We will use robust standard errors to account for clustering within village cluster
Outline stata code For analysis: For model checking:	<pre>stset outdate, f(hosp==1) enter (max(dob+1, date_enrol) /// exit (min (dnasc+60, date_mobileteam) origin(dob) stcox random, strata(sex reg prmorlev) vce(cl regam) estat phtest, detail† stphplot, strata(random) adj(sex reg prmorlev) stcox random, strata(sex reg prmorlev) vce(cl regam) tvc(random) texp(_t) *reg=region, prmorlev=pre-study mortality level, regam=village cluster</pre>

† If the proportional hazards assumption is not fulfilled we will still report the marginal hazard ratio but it will be supplemented by hazard ratios for two-three categorized time periods.

Severe morbidity

We will evaluate the effect on severe morbidity considered as the composite outcome of non-accidental death and non-accidental hospital admission. Since it can be difficult to distinguish between hospital admissions and outpatient contact through interviews, we have defined hospital admissions as an overnight stay in a health facility. Hospital admissions due to accidents are ignored but the follow-up time is (interval) censored while the child is admitted. The potential effect modifiers for the primary outcome specified in tables 3-6 will also be assessed for the composite outcome.

Table 8: Severe morbidity

Population	Identical to primary analysis of primary outcome
Observation period	From: Enrolment visit or 24 hours after birth, whichever comes last

	To: 60 days of life Censoring, first of: 
 - Visit by the BHP - Date of registering first non-trial vaccine given after enrolment - Death/Hospital admission due to accident - 60 days - Migration (migration out of the study area as per HDSS definition)
Time scale	Age
Failure definition	Death or first hospital admission
Statistical tool	Cox proportional hazards model
Stratification	We will employ models that allow for different baseline hazards according to sex, region and pre-study mortality level
Clustering	We will use robust standard errors to account for clustering within village cluster

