Outline stata code: For analysis For model checking	<pre> stset outdate, f(event==1) enter (max(dob+1, date_enrol) /// exit (min (dnasc+60, date_mobileteam) origin(dob) stcox random, strata(sex reg prmorlev) vce(cl regam) estat phtest, detail† stphplot, strata(random) adj(sex reg prmorlev) stcox random, strata(sex reg prmorlev) vce(cl regam) tvc(random) texp(_t) *reg=region, prmorlev=pre-study mortality level, regam=village cluster </pre>

† If the proportional hazards assumption is not fulfilled we will still report the marginal hazard ratio but it will be supplemented by hazard ratios for two-three categorized time periods.

Table 9: All-cause consultations

Population	Identical to primary analysis of primary outcome
Observation period	From: Enrolment visit or 24 hours after birth, whichever comes last To: 60 days of life Censoring, first of: 
 - Visit by the BHP - Date of registering first non-trial vaccine given after enrolment - 60 days

	
 - Migration (migration out of the study area as per HDSS definition) - Death - End of study
Failure definition	An out-patient consultation within the observation period
Statistical tool	Log-binomial regression
Adjustment	We will adjust the analysis for sex, region and pre-study mortality level
Clustering	We will use robust standard errors to account for clustering within village cluster
Stata code	Binreg cons random sex b1.reg pmorlev, rr vce(cl regam) *cons=out-patient consultation, reg=Region, pmorlev=Pre-study mortality level, regam=village cluster

Growth

Table 10: Mid-upper-arm circumference (MUAC)

Population	Identical to primary analysis of primary outcome
Observation time point	First visit by the mobile teams
Growth measures	MUAC will be analysed using the measured value
Statistical tool	Linear regression
Adjustment	We will adjust the analysis for MUAC at enrolment, age at MUAC measurement, sex, region and pre-study mortality level
Clustering	We will use robust standard errors to account for clustering within village cluster
Stata code	Regress MUAC random sex b1.reg pmorlev MUACenrol MUACage, /// vce(cl regam) *reg=region, pmorlev=pre-study mortality level, MUACenrol=MUAC at enrolment, MUACage= age at MUAC assessment, regam=village cluster

Table 11: Weight-for-age z-score

Population	Identical to primary analysis of primary outcome
Observation time point	First visit by the mobile teams

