Failure definition	Death due to: Malaria, Respiratory Infection, Sepsis, Gastrointestinal disease, Other
Statistical tool	Cox proportional hazards model
Stratification	We will employ models that allow for different baseline hazards according to sex, region and pre-study mortality level
Clustering	We will use robust standard errors to account for clustering within village cluster
Outline stata code For analysis: For model checking:	<pre>stset outdate, f(event==1&cause==X) enter (max(dob+1, date_enrol) /// exit (min (dnasc+60, date_mobileteam) origin(dob) stcox random, strata(sex reg prmorlev) vce(cl regam) estat phtest, detail† stphplot, strata(random) adj(sex reg prmorlev) stcox random, strata(sex reg prmorlev) vce(cl regam) tvc(random) texp(_t) *reg=region, prmorlev=pre-study mortality level, regam=village cluster</pre>

† If the proportional hazards assumption is not fulfilled we will still report the marginal hazard ratio but it will be supplemented by hazard ratios for two-three categorized time periods.

In sensitivity analyses, we will furthermore, assess whether the conclusions are robust to the following:

- Censoring follow-up at general health intervention campaigns (e.g. OPV campaigns)
- Altering the population to using an intention-to-treat approach, including all children, who had a home visit by a study nurse (i.e., including children who did not receive assigned treatment, children who were not enrolled because they were moribund, or who did not accept to participate).

- Altering the outcome from non-accidental mortality to all-cause mortality including also deaths due to accidents.
- For the non-accident hospitalisations, we will perform the analyses allowing for repeated hospitalisations. A child will return to the at-risk population the day after discharge from the hospital.

References

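### Table 13 of the SAP defines failure as cause-specific death, but its outline code uses `event`, Table 8's indicator for death or first admission; and the cause-specific admissions named in protocol 5.7.7 have no analysis in the SAP

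*SAP*

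**What the plan says.** The SAP's sensitivity section (Appendix 2, section 5) opens with Table 13, Cause-specific death. Its written failure definition is "Death due to: Malaria, Respiratory Infection, Sepsis, Gastrointestinal disease, Other". Its censoring list has five items: a BHP visit, 60 days, accidental death, the first non-trial vaccine and migration. Hospital admission is not among them. The outline code begins "stset outdate, f(event==1&cause==X) enter (max(dob+1, date_enrol".

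The other survival analyses of the SAP each carry their own indicator:

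- Table 2, primary outcome, death: "stset outdate, f(dead==1) enter (max(dob+1, date_enrol"
- Table 7, hospital admission: "stset outdate, f(hosp==1) enter (max(dob+1, date_enrol"
- Table 8, severe morbidity, with failure defined as "Death or first hospital admission": "stset outdate, f(event==1) enter (max(dob+1, date_enrol"

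The legend under the Table 13 code explains only three variables: "reg=region, prmorlev=pre-study mortality level, regam=village cluster". Neither `event` nor `cause` is defined there or elsewhere.

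Protocol section 5.7.7 says the sensitivity analyses will assess "whether we can identify if OPV and BCG prevents cause-specific hospitalisations or deaths (for details, see appendix: analysis plan"). In SAP section 5 the only item on admissions is an analysis of repeated hospitalisations, which is not split by cause.

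**The concern.** The code in Table 13 does not select what the table says it selects. A death-only indicator already exists in Table 2, and Table 13 uses the composite's indicator instead. A programmer who builds `event` and `outdate` once for Table 8 and reuses them here would produce hazard ratios labelled as cause-specific mortality from data set up for death or first admission.

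Table 13 is the SAP's only outcome analysis split by cause, so it is where a reader would look for which infections the vaccines act on. The companion question, cause-specific admission, is raised in the protocol and sent to the SAP for details, but the SAP gives none.

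**Working it through.** No figure in the plan depends on this point, so the check sets text against code and follows example records through each reading.

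**Step 1. Indicator against definition.**

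| SAP table | Written failure | Indicator in code | Agree? |
|---|---|---|---|
| 2 | death | `dead==1` | yes |
| 7 | first hospital admission | `hosp==1` | yes |
| 8 | death or first admission | `event==1` | yes |
| 13 | death, by cause | `event==1&cause==X` | no, if `event` means what it means in Table 8 |

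**Step 2. Example records.** Suppose `event` and `outdate` are built as in Table 8, so that `outdate` is the date of the first event, and no other censoring comes first. Two codings of `cause` are possible: cause of death only, or cause of whichever event came first.

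| Record | Written definition | `cause` = cause of death only | `cause` also filled in for admissions |
|---|---|---|---|
| Dies of sepsis at home, day 5 | sepsis death, day 5 | same | same |
| Admitted with malaria, day 20, survives | no failure, follow-up continues | no failure, but follow-up ends on day 20 | malaria death, day 20 |
| Admitted with gastrointestinal disease, day 10, dies of sepsis, day 30 | sepsis death, day 30 | sepsis death, dated day 10 | gastrointestinal death, dated day 10 |
| Admitted day 20, dies after day 60 | no failure in the window | can become an in-window death dated day 20 | in-window death dated day 20, under the admission's cause |

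Only the first record is right under both codings. Restricting `cause` to cause of death removes the false deaths among survivors. It does not correct the dates of deaths that follow an admission, and it does not restore the follow-up that surviving admitted infants lose.

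**Step 3. The correction.** With `dead==1&cause==X`, a surviving admitted infant is never a failure under either coding. With `outdate` also set to the mortality exit date of Table 2, an admission no longer ends follow-up or dates a death.

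**Step 4. Can it be sized?** Protocol section 5.3 gives 2.4% composite events, a 40% reduction and 6666 children. Taking 2.4% as the control risk and 3333 children per arm:

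- control: 3333 × 0.024 = 80
- intervention: 3333 × 0.024 × 0.6 = 48
- total: 128 children with a composite event

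The documents do not say how many of these die. As an assumption only, let 25%, 50% or 75% die within the window. Deaths are then 32, 64 or 96, and surviving admitted infants 96, 64 or 32. If `cause` were filled in for every admission, failures summed over causes would be 128/32 = 4.0, 128/64 = 2.0 or 128/96 = 1.33 times the true number of deaths. If `cause` is cause of death only, no surviving infant is added. The range runs from none to several-fold on inputs the plan does not supply, so it is no estimate of the error.

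**Step 5. Protocol 5.7.7 against the SAP.** The protocol names hospitalisations and deaths by cause. The SAP has a table for deaths by cause and none for admissions by cause. This gap exists however the Table 13 code is read.

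**The case against.** The best defence is that the written specification is clear and correct. Title, failure definition and censoring list all say death. The code is labelled as an outline and could not run as printed: `X` is a placeholder, the parentheses of `enter` and `exit` do not balance, and `dob` and `dnasc` both appear for what seems to be the date of birth. The name `outdate` serves Tables 2, 7, 8 and 13 despite their different failures, so it must be rebuilt for each analysis, and `event` may be just as generic. This stands as a reason to rate the point low. It does not remove the conflict, because no text says that `event` is redefined as death for Table 13, and Table 8 is the only guide to its meaning.

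Three stronger readings are tempting, and the documents support none of them.

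- A reader might infer that surviving admitted infants are certain to be counted as deaths. That requires `cause` to be filled in for admissions, which the SAP does not say.
- A reader might infer that the resulting hazard ratios would consist largely of admissions. Without a split of deaths and admissions, that cannot be known.
- A reader might infer that the hazard ratios would be pulled toward 1. This needs an effect on death and none on admission. With hazard ratios of 0.60 for death and 1.0 for admission, and deaths making up 30%, 50% or 70% of first events, the pooled value would be about 0.88, 0.80 or 0.72. Total events would then be 80 + 80 × 0.88 = 150, 80 + 80 × 0.80 = 144 or 80 + 80 × 0.72 = 138. None of these is the 128 that follows from a 40% reduction in the composite. The plan posits 40% for mortality (protocol section 4) and 40% for the composite (section 5.3), which together imply about 0.60 for admissions and essentially no dilution.

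It is also fair to say that protocol 5.7.7 is tentatively worded. Removing the mention of hospitalisations would reconcile the two documents as well as adding an analysis would.

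**Conclusion.** The conflict between code and definition is real. As written, Table 13 takes failures from the indicator that Table 8 uses for death or first admission.

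The wrong dating of deaths after an admission and the lost follow-up of surviving admitted infants rest on one assumption: `event` and `outdate` are built as in Table 8. Counting surviving infants as deaths rests on a second: `cause` is also filled in for admissions. The size of the error cannot be stated from the documents.

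The missing counterpart to the cause-specific hospitalisations of protocol 5.7.7 rests on neither assumption.

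Severity is minor. Table 13 is a sensitivity analysis, for which SAP Appendix 1, section 3, sets statistical significance aside. The trial's main conclusion rests on the primary analysis, which is coded with `dead==1`. No primary estimate, sample size or power figure changes.

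**What to change.** 1. In Table 13 replace the failure expression with `f(dead==1&cause==X)`, set `outdate` to the mortality exit date used for Table 2, and define `cause` in the legend as cause of death. This changes one line of code and adds one definition. It needs no new data.

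2. Reconcile protocol 5.7.7 with the SAP in one of two ways:
   - Add a cause-specific admission analysis with `f(hosp==1&cause==X)` on the Table 7 window, using a separately defined cause of admission and reporting it apart from the deaths. Protocol section 5.5.2 says the admission questionnaire records timing, symptoms, duration and place, and mentions no diagnosis. A prespecified rule from symptoms to cause groups is therefore needed, and writing it is the main cost. It also adds one more set of exploratory estimates.
   - Remove cause-specific hospitalisations from 5.7.7. This costs a wording change and gives up the analysis.
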